Title: Mindfulness-Based-Cognitive-Intervention for African Caribbean Men with Erectile Dysfunction

Study Protocol: ethically approved 20/01/2021

Study commencement: 01/10/2022

Study completion: 01/03/2023

Study protocol including statistical analysis plan

Methods

Design

A mixed study approach was used including a randomised controlled study with an experimental and waitlist control group. Further, a summative content analysis was conducted based on participant feedback responses. Participants were randomly allocated to one of two groups, group 1 (the experimental group receiving MBCI) and group 2 (the control waitlist group). The two groups were compared for differences in MBCI effectiveness in relation to sexual functioning, mindfulness, well-being and sexual self- efficacy (Kendall., 2013). A snowballing sampling method using social media including for example WhatsApp, TikTok, LinkedIn, Facebook was used to research sensitive issues among populations that might be difficult to reach (Browne, 2005). Participants A google form was developed where a link to the study contents was made accessible via Facebook, LinkedIn, Reddit and Twitter. All participants included 68 African Caribbean men with ED aged 18 years and above. Of the sample, 34 had been randomly allocated to group 1 and 34 to group 2. Participants had access to a password-protected laptop/computer and understand English at a suitable level. Further, participants were registered with a GP service (GP will be informed as this is an intervention). Sexuality and the individuals partnered status did not form part of the exclusion criteria. Those without ED, taking prescription medication including Viagra and were not registered with a GP were excluded from this study.

Assessment tools

Demographic Information Demographic information included ethnicity, partnered status, sexuality, age, employment status, children, cancer type, cancer treatment used, other health concerns, sexual difficulties, prescription medications and substance use including alcohol consumption and smoking, and levels of exercise.

The International Index of Erectile Function (IIEF-5) Questionnaire (Rhoden et al., 2002)

Consists of five questions with five response categories measuring erectile functioning. For the purpose of this study, erectile functioning and satisfaction were measured. Response categories

ranged from 0=no sexual activity to 5=almost always/always. Though response categories for each question varied including 0= very low to 5 very high. Scores 5-7 are suggestive of severe erectile dysfunction; and between 22-25 no erectile dysfunction.

The Sexual Self-Efficacy Erectile tool (SSES-E; Libman et al.,1985)

This is a 25-item questionnaire which focuses on sexual confidence and behaviour change associated with therapy. Participants' responses are measured via a 10-item scale ranging from 10 to 100. Here, 10 is the lowest level of self-efficacy and 100 is the highest. There are no reverse questions. The Cronbach's alpha for men with erectile difficulties is $\alpha = 0.88$ (high) and for men without erectile difficulties, $\alpha = 0.62$ (low to moderate). There is no other sexual self-efficacy questionnaire which has been developed for men. Adjustments to this questionnaire had been made in which less than 5% of the original questionnaire remained.

The Short Warwick-Edinburgh Mental Wellbeing Scale (SWEMWBS) (Tennant et al., 2007)

A positively worded seven item questionnaires with five response categories measuring functioning and feeling aspects of wellbeing. The response categories are 1=none of the time to 5=all of the time. Cronbach alpha 0.89-0.91. Scores range from 7 to 35 where the latter is the highest level of wellbeing.

The Cognitive and Affective Mindfulness Scale-Revised (CAMS-R; Feldman et al., 2007)

This is a 10-item measure with four response categories 1= rarely/not at all to 4 = almost always, with higher scores indicating higher levels of mindfulness (range 4-40). An example question is: "I can accept things I cannot change". Cronbach's alphas ranged between 0.82 and 0.84. Questions used in the content analysis A series of questions were asked throughout the duration of the MBCI. Participants were encouraged to leave one feedback per question to ensure that the team got a sense of the group's thoughts and feelings about the intervention collectively, rather than a disproportionate number of respondents.

The feedback outcome was obtained using Mentimeter, then coded and inputted into SPSS.

- Week 0: Question 1: What are your thoughts about receiving this MBCI?

Question 2: If you had a choice of practitioner who was going to deliver this intervention, what would your preferences be?

Question 3: What are your thoughts about your current erectile functioning?

- Week 4: Question 4: How is your erectile functioning now at the end of this MBCI?

Question 5: What are your experiences of receiving this intervention?

- Week 8: How is your ED at follow-up?
- Question 7: Any thoughts about whether you will continue to practise mindfulness to help your ED?
- Question 8: If you had an opportunity to receive this intervention again, would you prefer it delivered online or in person?
- Question 9: Would you have preferred this intervention to be delivered over a longer duration?
- Question 10: Is there anything else you would like to add about your experiences of this MBCI?

(b) Intervention developed for this study

The development of the MBCI has been based on a behavioural taxonomy using the BCTTv1 (Michie et al., 2016). Tables 1 and 2 include the mapping and links between these domains as the developing intervention.. In total, 16 domains have been included in the development of this intervention. Of these, 26 out of the 93 BCTs listed in the BCTv1 taxonomy were identified. Table 1: Behaviour Change Techniques in Each Component of the online MBI BCT BCT Principle Researcher Education Research Mindfulness Mindfulness Domain sessions assistants box practitioner Techniques within this Intervention target BCT taxonomy RCT Cognitive Psychoeducation Understanding ED 1.1, 1.2, 4.1, 4.3, 7.1, 9.1, 11.2, 13.2, 15.4 Emotional, physical, behavioural 1.3, 1.4, 1.7 and cognitive. Sexual self-efficacy Being sexually confident 1.2, 1.4, 1.9, 2.3, 11.2, 15.3 16.2 Cognitive reframe/self talk Challenging thoughts associated 4.3, 11.2, 13.2, 15.4 with sexual difficulties Behavioural Reward and reinforcement Encourage new behaviour coupled 1.2, 1.4, 4.1, 8.1, 8.2 with positive feedback 10.7, 10.10, 11.2, 14.4, 15.2 Self-care Behaviours which promote physical 3.1, 10.4, 13.1, 13.4 mental and emotional well-being Self-monitoring Monitor behaviour towards goals 1.1, 1.2, 1.3, 1.4, 1.9, 2.2, 2.3, 2.7 Creating a suitable behaviours which promote 12.5 environment relaxation and ambience MBCT Providing group support Creating a supportive environment 3.1, 10.4, 13.1, 13.4 and altruism encouragement and positive reinforcement Understanding emotions Recognising and developing emotions 1.2, 3.1, 5.6, 8.1, 11.2 and coping strategies 12.4 Goal setting/smart goals SMART goals for ED 1.1, 1.2, 1.3, 1.4, 1.9, 2.2 2.3, 2.7 Self-directed meditation Creating better awareness of 1.9, 4.1, 6.1, 8.1, 11.2, 15.2 body, mind and breathing Body scan Bringing attention and awareness 4.1, 6.1, 8.1, 11.2, 15.2 to different areas of the body. Top to toe. Mindfulness practices Being aware of the present moment 4.1, 6.1, 8.1, 11.2, 12.6 12.4, 15.2, 16.2 Mindfulness stretching Mind and body connection 4.1, 6.1, 8.1, 11.2, 12.6, 15.2, 16.2 Self-compassion Encouraging a positive self-identity 11.2, 13.1, 13.2, 13.4, 13.5

Procedure

In accordance with the BPS code of ethics and conduct (internet mediated, 2017) and following ethical approval from LMU ethics review panel, this clinical trial was registered with www.clinical.gov. Those interested in taking part signed a consent form which authorised the principal researcher to contact their General Practitioner (GP). Those accepted onto the programme provided written consent. Baseline questionnaire measures were taken at week 0 and repeated at weeks four and eight. The main exercises included mindfulness, breathing exercises, relaxation techniques, being mindful of the senses and the body and understanding enjoyable sex (adapted Bossio et al., 2018). Four one-to-two-hour online weekly group sessions took place over the duration of one month. Feedback on the intervention was sought throughout the intervention using Mentimeter, by which a content analysis of participants' experiences was conducted at each point. Participants were ensured confidentiality with respect to their engagement in the programme and anonymity. They were also reminded that they could withdraw from the study at any point and with no repercussions and did not have to answer all the assessment questions. Researchers in the team had experience of working in healthcare with vulnerable and diverse groups. They had been versed with the distress protocol prior to the research being started to support the recognition of distress among the participants. All responses generated from participants in this study were stored on a password protected

computer in accordance with the General Data Protection Regulation (2018); Data Protection Act (2018).

Statistical analyses

A mixed ANOVA was used to compare means of study variables measured across weeks 0, 4, and 8 weeks for both groups (experimental and control). A series of paired samples t-tests compared dependent variables pre- and post- tests and follow-up outcomes. Nonparametric Mann-Whitney was used to compare acquired and lifelong ED with substance use, medication use, alcohol consumption, exercise, and smoking. Feedback was taken from participants at weeks 0, 4 and 8 of the MBCI intervention and a summative content analysis using non parametric data analysis was used to analyse secondary data outcomes.

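### Men may withdraw or leave items blank, but the only between-arm analysis is a three-week mixed ANOVA that conventionally uses complete cases, so randomised men can be lost from the comparison

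*Combined protocol and SAP*

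**What the plan says.** - **Permission to leave gaps.** Under Procedure, of the men: "They were also reminded that they could withdraw from the study at any point and with no repercussions and did not have to answer all" of the assessment questions. No limit is put on either freedom.
- **Sample.** Under Participants: "All participants included 68 African Caribbean men with ED aged 18 years and above", allocated 34 to each group. No sample-size calculation or dropout allowance is given.
- **Outcomes.** The arms are compared on sexual functioning, sexual self-efficacy, well-being and mindfulness. Under Assessment tools these are measured by the IIEF-5 (5 items), SSES-E (25 items), SWEMWBS (7 items) and CAMS-R (10 items).
- **Timing.** "Baseline questionnaire measures were taken at week 0 and repeated at weeks four and eight".
- **Analysis.** Under Statistical analyses: "A mixed ANOVA was used to compare means of study variables measured across weeks 0, 4, and 8 weeks for both groups". Then: "A series of paired samples t-tests compared dependent variables pre- and post- tests and follow-up outcomes". The Mann-Whitney tests compare acquired with lifelong ED, and the feedback goes to a content analysis, so neither compares the arms on these scales.
- **What is absent.** Neither the scale descriptions nor the analysis section gives a rule for a blank item, a missed week or a withdrawal, or defines an analysis population.

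**The concern.** The plan grants men a freedom that its analysis does not accommodate. A conventional mixed ANOVA needs a score at every week, so one gap removes the man's other two scores on that scale as well. Randomisation balances the 34 and 34 men allocated; it does not protect a comparison of whoever happens to be complete.

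The questions are sexual and sensitive, and one arm attends weekly group sessions while the other waits. It is therefore plausible that completeness is related both to outcome and to arm. Each scale could also be analysed on a different subset of men. Because no rule is written down, the analyst would choose how to treat blanks after the data are in.

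**Working it through.** The plan gives no rate of skipping or withdrawal and no figure for numbers analysed, so there is nothing of its own to reproduce beyond 34 + 34 = 68. What follows shows how sensitive complete-case analysis is to small gaps.

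**Inputs from the documents.** N = 68; items per scale k = 5, 7, 10 and 25; three assessments. Answers needed per man over three weeks are 3k: 15 (IIEF-5), 21 (SWEMWBS), 30 (CAMS-R) and 75 (SSES-E), which is 141 in all.

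**Assumptions, not in the documents.** Each item is skipped independently with probability p; any blank makes that week's scale score missing; nobody withdraws.

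**Formula.** Expected complete cases = 68 × (1 − p)^(3k).

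| Scale | p = 0.5% | p = 1% | p = 2% |
|---|---|---|---|
| IIEF-5 | 68 × 0.928 = 63 | 68 × 0.860 = 58 | 68 × 0.739 = 50 |
| SWEMWBS | 68 × 0.900 = 61 | 68 × 0.810 = 55 | 68 × 0.654 = 44 |
| CAMS-R | 68 × 0.860 = 59 | 68 × 0.740 = 50 | 68 × 0.545 = 37 |
| SSES-E | 68 × 0.687 = 47 | 68 × 0.471 = 32 | 68 × 0.220 = 15 |

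**Adding withdrawal.** If a further 10% of men withdraw (assumed), each figure is multiplied by 0.9. At p = 1% this gives about 53, 50, 45 and 29 in the order of the table.

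**Relaxing independence.** Suppose the same 1% average comes from one man in five, each skipping 5% of items. For SSES-E, complete cases = 68 × (0.8 + 0.2 × 0.95^75) = 68 × (0.8 + 0.2 × 0.021) = about 55, against 32 under independence.

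**Changing the SSES-E scoring.** If SSES-E is a mean of the answered items, a single blank neither voids nor lowers the score, and the item-level loss largely disappears.

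**What a model using partial follow-up would keep.** Take SSES-E at p = 1% with independent skips. One week is complete with probability 0.99^25 = 0.778. A man lacks both follow-up weeks with probability (1 − 0.778)² = 0.049. Expected men with a week-4 or week-8 score = 68 × (1 − 0.049) = about 65, against 32 with all three weeks.

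**The case against.** The strongest reply is that the plan is silent rather than wrong. It does not say that a blank voids a score or is summed as 0. Prorating, averaging the answered items or imputing are all left open, and the illustrated losses rest on assumed rates. Much of this stands, and it rules out several stronger readings that a reader might infer:

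- *Any blank must either drop a man or lower his score.* The documents do not force that choice. The risk of lowering is a possibility only: the IIEF-5 uses 0 as a valid code for no sexual activity, so a blank summed as 0 could pass for a real answer and cost up to 5 of 25 points.
- *Every outcome is a multi-item total.* The ranges given for IIEF-5, SWEMWBS and CAMS-R imply sums. SSES-E has only a response scale from 10 to 100, with no stated sum or mean. The feedback outcomes are not scale totals and lie outside the ANOVA.
- *A zero falls below the SWEMWBS floor of 7.* That floor belongs to the total; the item minimum is 1. With one blank summed as 0, the total runs from 6 to 30, nearly always inside the stated 7 to 35.
- *The loss favours the intervention.* If poorly functioning men drop out and session contact retains more of them in the MBCI arm, the waitlist mean rises and MBCI looks worse. The documents establish neither the mechanism nor the direction.
- *The SSES-E comparison loses more than half the men.* This needs 1% or more skipping, independence and any-blank-voids scoring together.

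The loss is also limited to the affected scale. A man can remain in a paired t-test that does not use the affected week. But those tests compare weeks, not arms, so they do not rescue the randomised comparison. Nor does leaving item scoring open help with a missed week or a withdrawal, which no item rule repairs.

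**Conclusion.** The point holds in this form: blanks and withdrawal are expressly allowed, the sole between-arm analysis of the four scales conventionally discards a man lacking any of three scores, and nothing elsewhere in the plan compensates. The resulting comparison need not be of the 34 v 34 randomised and can be biased in an unknown direction.

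The size cannot be determined from the documents. The table shows that small item-level gaps could matter, most for the 25-item SSES-E and least for the IIEF-5, if any blank voids a score. Losses would be smaller if skipping is concentrated in a few men or if SSES-E is a mean of answered items, and larger with withdrawals. The conclusion about the method rests only on the conventional complete-case behaviour of a mixed ANOVA, not on the assumed rates. It is a should-fix point: the gap is clear, its effect is unquantified, and a better method is cheap.

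**What to change.** 1. **Replace the mixed ANOVA** with a likelihood-based repeated-measures model with group, week, group-by-week and the baseline score. Include every randomised man with any week-4 or week-8 score, in his allocated group. A missing week-0 score entered as a covariate would drop the man again, so either model week 0 as a response with a mean common to both arms or state how a missing baseline is filled.
2. **State one missing-item rule per scale**, for example the mean of answered items when most are answered, rescaled to the scale's stated range, and otherwise missing. This requires saying whether SSES-E is a mean (10 to 100) or a sum (25 × 10 = 250 to 25 × 100 = 2,500). It also requires reconciling the CAMS-R range of 4 to 40 with ten items scored from 1, whose sum cannot be below 10.
3. **Keep a blank distinct from the valid IIEF-5 code 0** in the dataset.
4. **Report numbers analysed** by scale, week and arm.
5. **Add a simple sensitivity analysis** for data missing not at random, such as shifting the unobserved scores by a range of amounts, separately by arm.

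The cost is some analysis-plan wording and a few lines of code; no new data are needed. The downside is that the model assumes data are missing at random and proration assumes skipped items resemble answered ones, which is why item 5 is needed. The plan is written in the past tense, so if outcomes have already been examined the revised analysis should be labelled as specified afterwards.

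### The plan names no deciding term in the mixed ANOVA and no between-arm contrast or CI at week 4 or 8; its only time-specific score tests are within-person paired t-tests

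*Combined protocol and SAP*

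**What the plan says.** Under Design, the aim is between-arm: "The two groups were compared for differences in MBCI effectiveness in relation to sexual functioning, mindfulness, well-being and sexual self- efficacy". Under Participants: "Of the sample, 34 had been randomly allocated to group 1 and 34 to group 2". Under Procedure: "Baseline questionnaire measures were taken at week 0 and repeated at weeks four and eight".

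The Statistical analyses section handles the questionnaire scores in two sentences. The first is "A mixed ANOVA was used to compare means of study variables measured across weeks 0, 4, and 8 weeks for both groups". The second is "A series of paired samples t-tests compared dependent variables pre- and post- tests and follow-up outcomes".

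The rest of that section does not compare the randomised arms on these scores. The Mann-Whitney test sets acquired against lifelong ED, and the content analysis of participant feedback is not described as an arm comparison. No significance level, effect size, SD, correlation or power figure appears anywhere.

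**The concern.** A two-group, three-visit mixed ANOVA yields a group term and a group-by-time term. Both are valid randomised comparisons, but they answer different questions. The group term averages all three visits, including week 0, when nobody has been treated. The group-by-time term asks whether the difference between the arms changes over the visits. Neither says at which week the arms differ or by how much, and the plan specifies no between-arm contrast to follow them.

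What the plan does specify by time is a set of paired t-tests. These test change against zero, so they respond to any drift that both arms share. The plan does not say whether they are run per arm or pooled, or what role they have.

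Two things are at stake. If the deciding term is not fixed, it can be chosen after the results are seen. And a reader who wants the effect at week 4 or week 8 is offered tests that do not measure it.

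**Working it through.** **Inputs.** From the documents: 34 per arm (Participants); visits at weeks 0, 4 and 8 (Procedure). Assumed, because the documents give none: normal scores with SD 1, equal correlation r between visits (0.3, 0.5, 0.7), two-sided 5%, no dropout, effect 0.6 SD. The plan has no figure of its own to reproduce.

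**Group term.** The expected difference is the mean over three visits: (0 + 0.6 + 0)/3 = 0.2 for an effect at week 4 only, and (0 + 0.6 + 0.6)/3 = 0.4 for both weeks. SE = √[(2/34)(1 + 2r)/3] = 0.177, 0.198, 0.217. The ratios are 1.13, 1.01, 0.92 and 2.26, 2.02, 1.84. Power comes from the non-central t with 66 df.

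**Group-by-time term.** The non-centrality is λ = (34/2) × Σ(dₖ − d̄)²/(1 − r). For week 4 only, the deviations are −0.2, 0.4, −0.2 and their squares sum to 0.24. For both weeks they are −0.4, 0.2, 0.2, which also sum to 0.24. So λ = 17 × 0.24/(1 − r) = 4.08/(1 − r) = 5.83, 8.16, 13.6 in either case. Power comes from the non-central F with 2 and 132 df.

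**Week-4 between-arm contrast adjusted for the week-0 score.** SE ≈ √[(2/34)(1 − r²)] = 0.231, 0.210, 0.173. The ratios 0.6/SE are 2.59, 2.86, 3.46.

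Simulation with 20,000 trials per setting agrees with these formulas:

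| Power, r = 0.3 / 0.5 / 0.7 | Group term | Group-by-time | Adjusted week-4 contrast |
|---|---|---|---|
| 0.6 SD at week 4 only | 20 / 17 / 15% | 56 / 72 / 92% | 72 / 80 / 92% |
| 0.6 SD at weeks 4 and 8 | 61 / 51 / 44% | 56 / 72 / 91% | 72 / 80 / 92% |

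With no effect, all three hold about 5%.

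**Precision.** The 95% half-width is 1.997 × SE ≈ 0.46, 0.42, 0.35 SD for the adjusted contrast. For change scores, SE = √[(2/34) × 2(1 − r)], which gives about 0.57, 0.48, 0.37 SD. With an assumed 20% loss (27 per arm) the adjusted half-widths are about 0.52, 0.48, 0.39 SD.

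**Secondary illustration: a week-8 claim.** Suppose a week-8 effect were claimed whenever the group-by-time term and the MBCI-arm week-8 paired test were both significant. The documents do not state this rule. Let the true effect be 0.6 SD at week 4 only, with equal drift in both arms. At r = 0.5 and drift 0.3 SD, the paired test alone has SE √[2 × 0.5/34] = 0.171 and ratio 0.3/0.171 = 1.75, although the arms do not differ at week 8. The simulated rates of the false claim are:

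| Drift in both arms | r = 0.3 | r = 0.5 | r = 0.7 |
|---|---|---|---|
| 0 | 4% | 4% | 5% |
| 0.1 SD | 5% | 7% | 11% |
| 0.2 SD | 10% | 16% | 29% |
| 0.3 SD | 18% | 30% | 54% |

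If the waitlist paired test must also be non-significant, the last row falls to 13–22%. A between-arm week-8 contrast stays at about 5% throughout.

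**The case against.** A reader might infer that the trial has no valid between-arm test, or that efficacy will be concluded from the paired t-tests. The documents support neither. The mixed ANOVA includes both arms, and either of its terms is a valid randomised comparison. The plan nowhere says that the paired tests decide efficacy.

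A fair defence goes further:

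- **The wording fits group-by-time.** Both groups and three visits suggest an ordinary group-by-time reading. That is plausible, but the term is not named, and a 2-df test still gives neither the week nor the size of a difference.
- **The means are there.** Arm-by-week means let anyone subtract to obtain a difference. This stands: what is missing is a declared contrast and its precision, not any possible point estimate.
- **The power gap depends on the scenario.** This also stands. A week-4-only effect is the least favourable case for the group term. For 0.6 SD falling to 0.3 SD by week 8, it is about 38–39% versus 44% at correlation 0.3, and 32–33% versus 58% at 0.5. For a sustained effect at correlation 0.3 the group term leads, 61% to 56%.
- **The week-8 false-claim rates need three things the documents do not supply:** the reading rule, an effect that has vanished by week 8, and equal drift. Without drift there is no inflation. Those rates are an illustration only.
- **Adjustment for baseline is a precision choice.** A change-score contrast is valid too, with a wider interval.

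**Conclusion.** The point holds as a gap in the analysis plan that should be fixed. The stated aim is a comparison of randomised arms, yet the deciding term is unnamed, no between-arm contrast or CI is specified at week 4 or week 8, and the only time-specific score tests are within-person. This conclusion is textual and does not depend on the simulations.

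The figures show direction and rough size under assumed effects, drifts and correlations. Neither ANOVA term is always ahead. In the two 0.6 SD scenarios tabulated, the baseline-adjusted week-4 contrast is at least level with both. That advantage requires the effect to be present at the week chosen.

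**What to change.** In the Statistical analyses section:

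- State that effectiveness is judged between the arms, with group-by-time as the overall test.
- In place of the paired t-tests as time-specific tests of effect, report the MBCI-minus-waitlist difference with 95% CI, adjusted for the week-0 score of the same scale, at week 4.
- Report the same at week 8 only if group 2 is still untreated then. The documents do not say when group 2 receives MBCI.
- State which week is the main contrast. Two contrasts on each scale also raise multiplicity across scales, which this change does not settle.
- Keep paired t-tests as per-arm description only.
- Label the contrasts post hoc if results have been seen. The text is in the past tense and gives completion as 01/03/2023, so this may well apply.

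**Cost.** A little more analysis on scores already collected. Before-after changes can no longer be reported as evidence of effect. The intervals are wide, as shown above, and will widen with missing data, since participants were told "they could withdraw from the study at any point and with no repercussions and did not have to answer all the assessment questions".

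### The only between-arm test of the scales is a mixed ANOVA that treats baseline as an outcome and names no treatment term; a baseline-adjusted model with one named contrast would be more precise at the same visit

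*Combined protocol and SAP*

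**What the plan says.** The Participants section reports that "34 had been randomly allocated to group 1 and 34 to group 2". The Procedure section makes week 0 the baseline: "Baseline questionnaire measures were taken at week 0 and repeated at weeks four and eight". The Statistical analyses section then says "A mixed ANOVA was used to compare means of study variables measured across weeks 0, 4, and 8 weeks for both groups", so the baseline becomes one of three outcome levels.

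The other analyses in that section do not compare the arms on the scales:
- Of the t-tests it says "A series of paired samples t-tests compared dependent variables pre- and post- tests and follow-up outcomes". A paired test measures change within a man.
- The Mann-Whitney test compares acquired with lifelong ED, not randomised groups.
- The content analysis covers feedback answers.

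No model term, contrast or visit is named as the treatment effect. No baseline covariate, significance level, effect size or missing-data rule is given. The Procedure section also records that participants were reminded that "they could withdraw from the study at any point and with no repercussions and did not have to answer all the assessment questions".

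**The concern.** In a mixed ANOVA with two arms and three times, two terms could be reported as the treatment result.

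- **Group main effect.** It averages over weeks 0, 4 and 8. Randomised arms have the same expected score at week 0, so a constant post-baseline difference is diluted to two thirds.
- **Group-by-time interaction.** It is not diluted. It uses change from baseline without adjustment and spreads the test over two degrees of freedom.

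Neither makes best use of the baseline. With the term left open, nothing in the plan prevents a choice between them after the results are seen.

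A conventional mixed ANOVA also keeps only men with all three scores. Since men may withdraw or leave questions blank, it can discard men who gave usable follow-up data.

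**Working it through.** The plan has no sample-size or power figure to reproduce.

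**Inputs.** From the documents: 34 men per arm and visits at weeks 0, 4 and 8. Assumed, because the documents give none: SD 1; the same correlation r between any two visits, r = 0.5/0.6/0.7; an effect of 0.6 SD at weeks 4 and 8; two-sided 5% tests; independent men. Triplets below follow that order of r.

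**Standard errors.** The variance of an arm difference is 2V/34.

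| Contrast | V | V at r = 0.5/0.6/0.7 | SE | Estimates |
|---|---|---|---|---|
| Group main effect (weeks 0, 4, 8) | (1+2r)/3 | 0.667/0.733/0.800 | 0.198/0.208/0.217 | (0+0.6+0.6)/3 = 0.40 |
| Week-4 change | 2(1−r) | 1.00/0.80/0.60 | 0.243/0.217/0.188 | 0.60 |
| Week-4 score adjusted for week 0 | 1−r² | 0.75/0.64/0.51 | 0.210/0.194/0.173 | 0.60 |

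Change against adjusted, the variance ratio is 2(1−r)/(1−r²) = 2/(1+r) = 1.33/1.25/1.18. It exceeds 1 for every r below 1, whatever the effect size. The 95% CI half-widths are about 0.48/0.43/0.38 SD for change and 0.42/0.39/0.35 SD for the adjusted contrast.

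**Interaction.** The noncentrality is (34/2) × 0.6² × (2/3)/(1−r) = 4.08/(1−r) = 8.16/10.2/13.6, on 2 and 132 df.

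**Power, complete data (simulated).** The formulas agree to about one point.

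| Test | Power, % |
|---|---|
| Group main effect | 51/47/44 |
| Two-df interaction | 71/81/91 |
| Adjusted week-4 contrast | 81/87/92 |

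At the same visit, unadjusted week-4 change has 68/78/88% by formula, against 80/86/92% adjusted.

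**Choosing the term afterwards.** In simulated null trials, counting a success if either the main effect or the interaction reached p<0.05 gave 9.9/9.8/9.5% false positives on one scale. Two independent tests would give 1−0.95² = 9.75%.

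**Missing scores (assumed rates, independent at each follow-up visit).**
- 10% per visit: 68×0.90² = 55 men are complete and 68×(1−0.10²) = 67 have a follow-up score. Power is 61/72/83% for the interaction and 75/83/90% for the model.
- 15% per visit: 68×0.85² = 49 against 68×(1−0.15²) = 66. Power is 56/65/79% against 75/80/88%.
- With no true effect and 10% missing at random, rejection rates were 4.3–5.1% and 5.0–5.4%.

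**Timing of the effect (complete data).**
- Fading from 0.6 to 0.2 SD by week 8: interaction 60/71/82%, week-4 contrast 80/86/92%.
- Late, 0.2 then 0.6 SD: interaction 59/71/82%, week-4 contrast 15/18/19%.

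**Selective dropout (an example, not a finding about this trial).** Suppose MBCI men with below-average week-4 change miss week 8 40% of the time, other MBCI men never, and controls 10%. Among completers the week-4 contrast is 0.80/0.78/0.76 instead of 0.60, and the interaction rejects a true null 9/10/8% of the time. The model gives 0.60 and about 5%.

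**The case against.** The mixed ANOVA is not invalid: its interaction is unbiased under randomisation, and the dilution matters only if the main effect is read, which the plan does not say. The power table also mixes two changes, naming a one-df contrast and adjusting for baseline. A one-df contrast inside the existing ANOVA (mean of weeks 4 and 8 minus week 0) has simulated power of 82/89/95% when the effect is constant, so naming a term alone recovers the headline power. Against the interaction, the gain is only about one point at r = 0.7. Naming week 4 is costly if the effect comes late. The missingness rates are assumed, and no dropout is reported.

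Much of this stands, and it limits the claim to precision and an unnamed estimand. It does not remove the point:
- The unadjusted averaged contrast falls to 47/56/67% if the effect fades, against 79/86/92% for the adjusted week-4 contrast in the same simulation.
- At any given visit, adjustment lowers the variance for every r below 1.
- Naming a term is needed on either view.

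Three further limits apply. The documents do not say when the waitlist arm receives the intervention, so the chosen week needs a stated reason. Naming one contrast still leaves four constructs with no primary scale. Sessions were held in groups, so outcomes in the MBCI arm may be correlated; neither these calculations nor the proposed model allows for that, and the absolute powers may be optimistic.

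**Conclusion.** The concern holds. The only between-arm analysis of the scales uses baseline as an outcome and leaves the treatment term open. Baseline adjustment at the same visit cuts the variance to (1+r)/2 of that for change: 75/80/85% at r = 0.5/0.6/0.7. The advantage over the interaction is moderate at r = 0.5, small at 0.7, and larger with missing scores. The advantage over the main effect is large throughout. These powers rest on the assumed effect, correlation and missingness; the direction of the same-visit gain in large samples rests only on r below 1 and equal variances. At very high correlation the gain nearly vanishes: at r = 0.9 it is 5% of variance, against about 1.6% lost in estimating the covariate.

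The demonstrated harm is lost precision and an open choice of test. Bias arises only if dropout is related to outcome. The analysis should be changed, but the plan's ANOVA is inefficient and under-specified, not wrong in principle.

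**What to change.** Replace the mixed ANOVA with a likelihood-based repeated-measures model (REML, unstructured covariance) of the week-4 and week-8 scores:

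- **Fixed effects:** arm, week, arm by week, and the week-0 score of the same scale.
- **Analysis set:** men in their allocated arm, including everyone with any post-baseline score. If week-0 scores are missing, keep week 0 in the outcome vector with a common baseline mean so that those men stay in.
- **Primary contrast:** the arm difference at week 4, unless the sponsor expects a late effect and can justify week 8. The content-analysis questions place the end of the programme at week 4 ("How is your erectile functioning now at the end of this MBCI") and treat week 8 as follow-up ("How is your ED at follow-up"). State when the waitlist arm received the intervention as part of the reason for the choice.
- **Reporting:** the other visit as secondary, with 95% CIs for both.
- **Scoring:** a rule for partly blank questionnaires, which the model does not supply.

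This needs no new data and slightly more analysis work. The title block gives "Study completion: 01/03/2023", so it would be a reanalysis labelled as revised, and it cannot undo a choice already made. The model assumes data are missing at random. Men with no follow-up score are lost, or add no treatment information if week 0 is in the outcome vector. Power is low if the effect appears only after the named visit.
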